4.1 Adverse Event Reporting and Monitoring

4.1.1 Definition

A reportable adverse event is any untoward medical occurrence in a study participant, irrespective of whether or not the event is considered treatment-related, that occurs 12 hours prior, during, or the day after each exercise session, except for hypoglycemia, hyperglycemia, injection-related, and exercise-induced events which are only reported as adverse events when the criteria described below are met.

Hypoglycemic events are recorded as Adverse Events if the event required IV dextrose or IM glucagon to treat.

Hyperglycemic events are recorded as Adverse Events if evaluation or treatment was obtained from a health care provider or if the event involved DKA, as defined by the Diabetes Control and Complications Trial (DCCT) and described below, or in the absence of DKA if evaluation or treatment was obtained from a health care provider or an acute event involving hyperglycemia or ketosis.

Hyperglycemic events are classified as DKA if all of the following are present:

- Symptoms such as polyuria, polydipsia, nausea, or vomiting
- Serum ketones >1.5 mmol/L or large/moderate urine ketones
- Either arterial blood pH <7.30 or venous pH <7.24 or serum bicarbonate <15
- Treatment provided in a health care facility

Injection-related events are recorded as Adverse Events if sufficiently severe that treatment was given.

Exercise-induced events are recorded as Adverse Events if the subject falls during the exercise protocol or develops signs or symptoms of a myocardial infarction, poor perfusion (pallor, cyanosis), angina, pathologic arrhythmia, or another medical condition not expected to occur during or following the exercise.

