4.1.2 Recording of Adverse Events

Throughout the course of the study, all efforts will be made to remain alert to possible adverse events or untoward findings.

All adverse events whether volunteered by the participant, discovered by study personnel during questioning, or detected through physical examination, laboratory test, or other means will be reported on a web-based case report form specifically for adverse event reporting.

The study investigator will assess the relationship of each adverse event to be related or unrelated to study drug by determining if there is a reasonable possibility that the adverse event may have been caused by the treatment. Reasonable possibility is not the same as “any possibility.” The following should be considered when evaluating the relationship:

- Timing of event
- Patient’s history

- 472 • Prevalence of finding in population at risk
- 473 • Other possible causes - diseases, exposures, therapies, etc
- 474 • Known pharmacology of study drug (and control) or side effect of drug
- 475

476 The intensity of adverse events will be rated on a three-point scale: (1) mild, (2) moderate, or (3)
477 severe. It is emphasized that the term severe is a measure of intensity: thus, a severe adverse event
478 is not necessarily serious. For example, itching for several days may be rated as severe, but may not
479 be clinically serious.

480 Adverse events that continue after the study participant's discontinuation or completion of the study
481 will be followed until their medical outcome is determined or until no further change in the
482 condition is expected.

483 Each reported adverse event is reviewed by the Medical Monitor to verify the coding and the
484 reporting that is required. Adverse events will be coded using the MedDRA dictionary.

485 486 **4.1.3 Reporting Serious or Unexpected Adverse Events**

487 A serious adverse event is any untoward occurrence that:

- 488 • Results in death
- 489 • Is life-threatening (a non-life-threatening event which, had it been more severe, might have
490 become life-threatening, is not necessarily considered a serious adverse event)
- 491 • Requires inpatient hospitalization or prolongation of existing hospitalization
- 492 • Results in significant disability/incapacity
- 493 • Is a congenital anomaly/birth defect
- 494 • Could have resulted in death, be life-threatening, or require hospitalization without medical
495 or surgical intervention to prevent any of these events

496

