535 higher compared with the Xeris 0.5 mg and 1 mg groups. The incidences of all remaining AEs
536 were low and not notably different across treatment groups.

537
538 However, as reported by Haymond (15), when subcutaneous glucagon in dosages of 20–150 µg was
539 given to children to manage impending hypoglycemia due to gastroenteritis or poor oral intake of
540 carbohydrates, it did not result in a perceived worsening of the patient’s nausea, nor did it result in
541 emesis immediately after glucagon administration, as is commonly observed with the recommended
542 single large 500–1,000 µg rescue dose.

543
544 In Xeris’ completed Phase 2a safety/PK/PD study, Protocol No. XSMP-201, which tested 75–300
545 µg G-Pen Mini™ doses in adult T1D patients, neither nausea nor vomiting were observed with
546 doses of 75-150 µg. Nausea, but not vomiting was reported by 4/12 subjects given the 300 µg dose
547 (3 mild, 1 moderate). Since doses of subcutaneous G-Pen Mini™ (glucagon injection) given to
548 adults per this protocol will range from 75–300 µg, some nausea is possible, but the incidence is
549 expected to be relatively low and severe nausea is not expected.

550 Although available data from prior studies indicate that mini-dose glucagon is likely to successfully
551 treat mild to moderate hypoglycemia, this is not definitively proven. Therefore, there is a risk that
552 mini-dose glucagon will not work as well as glucose tablets or other oral carbohydrates and if this is
553 the case, severe hypoglycemia could result.

554 Endurance exercise, as will be performed in this study, may be associated with generalized fatigue
555 and mild to moderate hypoglycemia. In rare situations, exercise can promote myocardial infarction,
556 sudden cardiac death or arrhythmias. In persons who have proliferative retinopathy, exercise that
557 increases blood pressure significantly (>180 mmHg) can promote retinal bleeding (PMID:
558 21800941). Since all participants will be screened prior to the exercise test for diabetes-related
559 complications and glucose monitoring will be performed throughout the experiments, the risk of a
560 serious exercise-associated adverse event will be extremely remote.

561

562 The blood draws and IV placement could result in discomfort or bruising, or rarely, an infection or a
563 blood clot. Fainting may also occur. The exact blood volumes collected may vary according to

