6.3 Safety Analyses

697 Adverse events will be tabulated by strategy:

698

- 699 • Proportion reporting at least one adverse event
- 700 • Proportion with an adverse event thought by investigator to be related to strategy
- 701 • Proportion who stopped study treatment in response to an adverse event
- 702 • Total number of adverse events reported
- 703 • Number of serious adverse events reported
- 704 • Number of non-serious adverse events reported

705

706 Adverse events will be tabulated by MedDRA categories with frequencies compared between
707 strategies. Similar models and diagnostics will be performed as described for the efficacy outcomes
708 above.
709
710

711 **CHAPTER 7: DATA COLLECTION AND MONITORING**
712

713 **7.1 Data Collection**

714 Data will be collected directly on electronic case report forms and will be considered source
715 documents when data are directly entered. Other data will be collected from participant logs,
716 downloads of devices and from laboratories processing the samples.
717

718 **7.2 Quality Assurance and Monitoring**

719 Designated personnel from the Coordinating Center will be responsible for maintaining quality
720 assurance (QA) and quality control (QC) systems to ensure that the trial is conducted and data
721 are generated, documented and reported in compliance with the protocol, GCP and the applicable
722 regulatory requirements.
723

724 A risk-based monitoring (RBM) plan will be developed and revised as needed during the course
725 of the study. The RBM plan will focus mainly on data related to eligibility, adverse events and
726 the primary efficacy analysis. As much as possible, remote monitoring will be performed in
727 real-time, with on-site monitoring performed to evaluate the verity and completeness of the key
728 site data.
729

730 Xeris, the Jaeb Center for Health Research, or their representatives may visit the study facilities
731 at any time in order to maintain current and personal knowledge of the study through review of
732 the records, comparison with source documents, observation and discussion of the conduct and
733 progress of the study.
734
735

736

CHAPTER 8: REFERENCES

737

738 1) Chu L, Hamilton J, Riddell MC (2011) Clinical management of the physically active patient
739 with type 1 diabetes. *Physiol Sports Med* 39: 64–77.

740

741 2) West DJ, Morton RD, Bain SC, Stephens JW, Bracken RM (2010) Blood glucose responses

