119 The secondary outcomes will largely be examined in a descriptive manner. Summary statistics
120 will be calculated by treatment strategy. For binary variables, percentage of participants
121 developing the outcome, with 95% confidence interval, will be calculated by strategy. Strategy 3
122 will be compared with each of the other strategies in secondary analyses.

123

124 Tests of significance will also be obtained using a 2-sided alpha of 0.05. For binary variables, a
125 generalized linear mixed model with a logistic link function for a binary outcome will be fit to
126 assess differences between strategy 3 and each of the other strategies. The model will be
127 adjusted for baseline glucose and any period effect. For continuous variables, a repeated
128 measures linear regression model will be fit adjusting for period and where applicable the
129 baseline value. One model will be run per outcome measure, with multiple pairwise comparisons
130 from the same model. Regression diagnostics will be performed and if the distribution of
131 residuals is skewed, non-parametric methods and transformations will be considered. No formal
132 correction will be made for multiple comparisons.

133

134

135 **3.5 Exploratory Analyses**

136 The following outcome measures may be explored:

- 137 • Carbohydrate intake (before, during and for 30 min post exercise)
- 138 • HR and ratings of perceived exertion
- 139 • Insulin and glucose counterregulatory hormones (glucagon, GH, catecholamines,
140 cortisol)
- 141 • Inflammatory cytokines (TNF α , IL-6)
- 142 • Metabolites (nonesterified fatty acids, β -hydroxybuterate, lactate)

143
144 **3.6 Additional Tabulations**

- 145 • Baseline characteristics
- 146 • Number of subjects who did not complete the study and reasons for discontinuation

147
148 **4.1 Safety**

149 Information from all subjects throughout the study will be used to assess safety.

150
151 **4.1.1 Adverse Event Definitions**

152 A reportable adverse event is any untoward medical occurrence in a study participant,
153 irrespective of whether or not the event is considered treatment-related, that occurs 12 hours
154 prior, during, or the day after each exercise session, except for hypoglycemia, hyperglycemia,
155 injection-related, and exercise-induced events which are only reported as adverse events when
156 the criteria described below are met.

157
158 Hypoglycemic events are recorded as Adverse Events if the event required IV dextrose or IM

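### Injection-related and exercise-induced events are screened by cause before they are recorded, so untreated injection-site pain is lost and the adverse event comparison between strategies can be distorted

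*Protocol*

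**What the plan says.** Protocol 4.1.1 opens with a broad rule: an event in the reporting window around a session counts "irrespective of whether or not the event is considered treatment-related". The same sentence then makes four exceptions: "except for hypoglycemia, hyperglycemia, injection-related, and exercise-induced events which are only reported as adverse events when the criteria described below are met". Two are glucose states. The other two are named by cause.

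The criteria for those two differ. For injections: "Injection-related events are recorded as Adverse Events if sufficiently severe that treatment was given". For exercise, an event counts if it is a fall, one of the listed cardiac or perfusion signs, or "another medical condition not expected to occur during or following the exercise". Neither section defines what makes an event injection-related or exercise-induced. SAP 4.1.1 carries the same clause ("injection-related, and exercise-induced events which are only reported as adverse events when" the criteria are met).

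Protocol 4.1.2 places attribution with the site: "The study investigator will assess the relationship of each adverse event to be related or unrelated to study drug". Protocol 6.3 and SAP 4.1.2 use the recorded events comparatively: "Adverse events will be tabulated by MedDRA categories with frequencies compared between" strategies, with models similar to those for efficacy.

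Protocol 3.2.2 gives a saline injection in the control session and strategy 1, so that the participant is blinded among control, strategy 1 and strategy 3. Strategy 2 is oral dextrose, with no stated injection, and lies outside the blinded set. Neither document says whether the person who records and attributes events is blinded.

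**The concern.** Attribution normally follows recording: the event is written down, then its relation to treatment is rated. Here, for two classes of event, a view about cause decides whether there is a record at all. Counts by strategy then depend on how symptoms were attributed and whether they were treated, as well as on how often they occurred.

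The symptoms exposed to this filter are those the protocol itself links to glucagon. In Protocol 4.2.1, injection-site pain was the most frequent adverse event in the Phase 2 rescue-dose study, and significantly more frequent with the manufacturer's product than with the marketed comparator. Nausea takes up most of the rest of that drug-risk discussion.

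At stake is the tolerability side of the comparison between glucagon and the alternatives. The primary glucose outcome is not affected.

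**Working it through.** The documents give no figure for adverse event recording or for nausea by strategy, so there is nothing to reproduce. The check is first a reading of the rule, then an illustration of size.

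**1. What happens to an untreated nausea episode**

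| Attributed to | Recorded? | Route exists in |
|---|---|---|
| Injection, if the term covers systemic effects | No, because untreated | Strategy 3, control, strategy 1 |
| Exercise, and thought expected | No | All four |
| Neither | Yes | All four |

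The same episode can be kept or dropped. The first route has no evident scope in strategy 2.

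**2. What happens to untreated injection-site pain**

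It falls plainly under the injection exception and is not recorded in any strategy.

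**3. Does later text recover a dropped event?**

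- Protocol 4.1.2 asks for every adverse event, however detected, to be reported, and for its relation to study drug to be rated. Both steps apply to events that already meet the definition in 4.1.1.
- The next-day call in Protocol 3.2.3 elicits adverse events, but no standard symptom question is set.
- Hypoglycemia and hyperglycemia are also excepted, but are captured separately as YSI outcomes (Protocol 6.2.3, SAP 3.4). Nausea and injection-site pain are in no outcome list, so adverse event recording is their only stated way into the analysis.

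**4. Effect on a comparison**

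Let p be the true proportion with the symptom and s the share of those events recorded, for glucagon (G) and a comparator (C). The recorded difference is

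D = p_G × s_G − p_C × s_C.

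If s is the same on both sides, D = s × (p_G − p_C): a true difference shrinks by the factor s, and none is created. If the shares differ, D can move either way.

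*Injection-site pain.* Strategy 2 has no stated injection, so p_C = 0 and D = s_G × p_G, which can only understate. Against control or strategy 1 with equal s, the difference is again multiplied by s; if no pain is treated, s = 0 and the table shows no difference whatever the truth. The documents give no rate for site pain, so no number is put in.

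*Nausea.* The only rate available is in Protocol 4.2.1: "Nausea, but not vomiting was reported by 4/12 subjects given the 300 µg dose" (3 mild, 1 moderate). That is 4/12 = 33.3%, exact 95% CI 9.9% to 65.1%. None was seen at 75–150 µg. For illustration, take p_G = 4/12 and assume p_C = 1/12; of 16 participants that is 16 × 4/12 = 5.33 and 16 × 1/12 = 1.33. All recording shares are assumptions.

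| s_G | s_C | Calculation (%) | D (points) |
|---|---|---|---|
| 1 | 1 | 33.3 − 8.3 | +25.0 |
| 0.5 | 0.5 | 16.7 − 4.2 | +12.5 |
| 0.5 | 1 | 16.7 − 8.3 | +8.3 |
| 0.25 | 1 | 8.3 − 8.3 | 0 |
| 1 | 0.5 | 33.3 − 4.2 | +29.2 |

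With equal true rates of 1/12, 20% or 1/3, shares of 0.5 (glucagon) and 1 (comparator) give spurious differences of −4.2, −10.0 and −16.7 points. Reversing the shares gives +4.2, +10.0 and +16.7. With 16 participants, one participant gained or lost moves a proportion by 1/16 = 6.25 points.

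**The case against.** The case on the other side is substantial.

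- **Nausea may not be caught by the injection exception.** It is named in neither exception. The injection findings described in Protocol 4.2.1 are local (pain, edema, erythema), so injection-related may mean local reactions only, with nausea recorded under the general rule. This is plausible, but the text does not say so, and on that reading site pain is still lost. The exercise route also remains open.
- **The sentence does not strictly contradict itself.** A reader might infer a contradiction between the broad rule and the exceptions. An explicit exception qualifies a rule, and exercise is common to all sessions rather than being the study treatment. This stands; the problem is the consequence of the exceptions.
- **Saline and participant blinding protect two of the three comparisons.** Against control and strategy 1 the same routes are open on both sides, so a spurious difference needs an assessor who knows or guesses the strategy. This stands, although assessor blinding is neither stated nor excluded, and equal loss still shrinks a true difference.
- **Few nausea events may occur.** Protocol 3.2.2 calls 150 µg likely within a possible 75–300 µg, and no nausea was seen at 75–150 µg. This stands. The site-pain finding likewise comes from rescue doses of 0.5 and 1.0 mg in healthy volunteers, so its frequency here is unknown.
- **Events are already actively sought.** Volunteered, elicited and examined findings are collected, and there is a next-day call. This helps detection but does not remove the filter on what is then reported.

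**Conclusion.** The concern holds as a flaw in the recording rule that can distort the safety comparison. Followed as written, the rule omits every untreated injection-site reaction. It also leaves the recording of untreated nausea to attribution, under two undefined terms.

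Distortion between strategies is most plausible for strategy 3 against strategy 2, where the injection route exists on one side only and the participant is not blinded. Against control and strategy 1 the main effect is to shrink a true difference, unless the assessor knows the strategy.

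A reader might go further and infer that the comparison is biased in a known direction, or that glucagon nausea will vanish from the table or appear only under glucagon. The documents do not support this. They do not say how nausea is to be classified or who is blinded, and such extremes need every event to be classified one way. The differences shown above rest on the 300 µg rate, an assumed comparator rate and assumed recording shares; they show sensitivity and are not forecasts.

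The change is worth making because it is cheap and these symptoms have no other route into the analysis.

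**What to change.** In Protocol 4.1.1 and SAP 4.1.1:

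1. Define the exceptions by kind of sign (for example, ordinary fatigue on exertion), not by presumed cause.
2. State that nausea, vomiting and injection-site reactions are recorded in every session, whether or not treated and whatever the suspected cause. Enter attribution afterwards in a separate field, and state whether the person who makes it is blinded to strategy.
3. Ask the same symptom question in all four sessions and on the existing next-day call.

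In Protocol 6.3 and SAP 4.1.2, tabulate these symptoms by strategy and by the three-point intensity rating that Protocol 4.1.2 already collects.

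The cost is a wording change in each document, one standard question, and more minor events to enter and code. There is also a transition cost. The SAP version history shows data collection in progress with no analyses performed, so a change would leave sessions under two rules, possibly within one participant. Sessions recorded under the present rule must be identified and reported as such. If the definition is left unchanged, the report should say that untreated injection-related events were not collected and that the by-strategy frequencies are to be read with that limit.

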1.4 Flow Chart of Exercise Sessions

182
183
184
185

186 **CHAPTER 2: PARTICIPANT ELIGIBILITY AND ENROLLMENT**

187
188 **2.1 Study Population**

189 The crossover trial will include 16 participants who complete the study. Participants may be
190 replaced if a participant does not complete the entire protocol. Each site is expected to have 8
191 participants completing the crossover trial, but this could be increased at a given site if necessary
192 to meet the recruitment goal.

193
194 **2.2 Eligibility**

195 To be eligible for the study, a participant must meet the following inclusion criteria and none of
196 the exclusion criteria:

197
198 **2.2.1 Inclusion Criteria**

- 199 1) Clinical diagnosis of presumed autoimmune type 1 diabetes, receiving daily insulin
200 2) Age 18-<65 years
201 3) Duration of T1D ≥ 2 years
202 4) Random C-peptide < 0.6 ng/ml
203 5) Using CSII (e.g., insulin pump) for at least 6 months, with no plans to discontinue pump
204 use during the study
205 6) Exercises regularly, i.e. ≥ 30 minutes moderate or more vigorous aerobic activity $\times \geq 3$
206 times/week
207 7) Body mass index (BMI) < 30 kg/m²
208 8) Females must meet one of the following criteria:
209 a. Of childbearing potential and not currently pregnant or lactating, and agrees to
210 use an accepted contraceptive regimen as described in the study procedure manual
211 throughout the entire duration of the study; or
212 b. Of non-childbearing potential, defined as a female who has had a hysterectomy or
213 tubal ligation, is clinically considered infertile or is in a menopausal state (at least
214 1 year without menses)
215 9) In good general health with no conditions that could influence the outcome of the trial,
216 and in the judgment of the investigator is a good candidate for the study based on review
217 of available medical history, physical examination and clinical laboratory evaluations
218 10) Willing to adhere to the protocol requirements for the duration of the study
219 11) Must be enrolled in the T1D Exchange clinic registry or willing to join the registry

220
221
222 **2.2.2 Exclusion Criteria**

- 223 1) One or more severe hypoglycemic episodes in the past 12 months (as defined by an
224 episode that required third party assistance for treatment)
225 2) Active diabetic retinopathy (PDR or VH in past 6 months) that could potentially be
226 worsened by exercise protocol
227 3) Peripheral neuropathy with insensate feet

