497 Serious or unexpected adverse events must be reported to the Coordinating Center immediately via
498 completion of the online serious adverse event form.

499
500 The Medical Monitor responsible for reviewing serious or unexpected adverse events is:

501
502 [name]., Ph.D.
503 Jaeb Center for Health Research
504 [name]
505 [name]
506 [contact]
507 [contact]
508 Email: [contact]

509
510 The Coordinating Center will notify all participating investigators of any adverse event that is
511 serious, related to the study drug or procedures, and unexpected. Notification will be made within
512 10 days after the Coordinating Center becomes aware of the event. The Coordinating Center also
513 will notify Xeris of any such events, who will be responsible for fulfilling reporting requirements to
514 the Food and Drug Administration (FDA).

515 Each principal investigator is responsible for informing his/her IRB of serious, related, and
516 unexpected adverse events and abiding by any other reporting requirements specific to his/her IRB.
517

518 **4.2 Risks**

519 **4.2.1 Potential Risks and Side Effects**

520 Glucagon has a long history of medical use in the U.S., and is currently marketed by Eli Lilly & Co.
521 as Glucagon for Injection [rDNA origin], and Novo Nordisk as GlucaGen® HypoKit®, both
522 reference listed drugs for treatment of severe hypoglycemia. Glucagon has a rapid onset of action
523 and an extremely short half-life, and its safety, efficacy and clinical pharmacology have been well
524 established.

525
526 In a Phase 2 study, Protocol No. XSGP-201, healthy, fasted adult volunteers were administered
527 rescue doses of Xeris G-Pen™ (glucagon injection) (0.5 mg and 1.0 mg) and Lilly Glucagon for
528 Injection [rDNA origin] (1.0 mg) in a randomized, crossover fashion. Overall, all Xeris and Lilly
529 treatments were well tolerated. There were no SAEs during the study, and all AEs observed were
530 transient and generally expected with rescue injections of glucagon. The most commonly reported
531 AE was injection site pain, and the incidence of this AE was significantly higher in the Xeris 0.5 mg
532 and Xeris 1 mg groups compared with the Lilly 1 mg group; however, edema and erythema at the
533 injection site occurred infrequently and did not vary significantly with treatment. Within the Lilly 1
534 mg group, the most commonly reported AE was nausea, the incidence of which was significantly

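### The adverse event table will not show non-serious hypoglycemia that needed another person's help but was treated orally, nor untreated injection-site reactions

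*Protocol*

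**What the plan says.** Protocol 4.1.1 starts from a broad definition of a reportable AE, then narrows it for four event types: "except for hypoglycemia, hyperglycemia, injection-related, and exercise-induced events which are only reported as adverse events when the criteria described below are met". Two of those criteria matter here. For hypoglycemia: "Hypoglycemic events are recorded as Adverse Events if the event required IV dextrose or IM glucagon to treat". For the injection: "Injection-related events are recorded as Adverse Events if sufficiently severe that treatment was given". SAP 4.1.1 carries the same text ("Hypoglycemic events are recorded as Adverse Events if the event required IV dextrose or IM" glucagon), and SAP 4.1.2 builds the by-strategy safety tables from events so defined.

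Three other places bear on the point.

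- Protocol 2.2.2, exclusion criterion 1, describes a severe hypoglycemic episode in the past 12 months as an "episode that required third party assistance for treatment". This is the only description of severe hypoglycemia in either document.
- Protocol 4.2.1 warns that mini-dose glucagon may work less well than oral carbohydrate and that, if this is "the case, severe hypoglycemia could result". Protocol 1.2.6 puts hypoglycemic events first among the main safety outcomes.
- Protocol 4.2.1 also summarises an earlier Phase 2 study of Xeris glucagon at rescue doses of 0.5 and 1.0 mg. The most frequent "AE was injection site pain, and the incidence of this AE was significantly higher in the Xeris 0.5 mg" and 1 mg groups than with the comparator glucagon.

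**The concern.** The hypoglycemia trigger depends on which treatment was used. An episode at home in which a family member had to help, and gave juice or tablets, fits the protocol's wording for a severe past episode but is not an AE on study. IV dextrose is unlikely to be at hand after discharge, so a trigger built on IV or IM treatment is least sensitive there. A reader of the AE table could see no hypoglycemia under a strategy although an assisted episode had occurred.

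The injection rule depends on treatment in the same way. A painful injection that nobody treats leaves no trace. Yet the design provides a good comparator: under Protocol 3.2.2, saline is injected in the control trial and strategy 1, with the participant blinded to strategy. Local tolerability of glucagon against saline could be compared within the same person, and the rule discards most of that information.

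**Working it through.** No power, rate or sample size figure is at issue. The check is to take each kind of event and ask where the documents would record it.

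| On-study event | In the AE tables? | Recorded elsewhere? |
|---|---|---|
| Hypoglycemia needing IV dextrose or IM glucagon | Yes (4.1.1) | Treatment record, if in session |
| Hypoglycemia meeting a seriousness criterion | Yes (Protocol 4.1.3 has no exception for hypoglycemia) | Serious event form |
| Glucose <70 mg/dL, exercise or early recovery | Only if one of the above | Yes, YSI secondary outcome |
| Glucose <70 mg/dL overnight | Only if one of the above | Yes, CGM secondary outcome |
| **Another person's help needed, oral treatment, not serious** | **No** | **Glucose value perhaps; need for help, no** |
| Nausea, vomiting | Yes (not among the four restricted types) | – |
| Injection-site reaction, treated | Yes | – |
| **Injection-site reaction, untreated** | **No** | **No** |

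Two rows are empty. The next question is whether other data fill them.

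**Assisted hypoglycemia.**

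1. The YSI and CGM outcomes (SAP 3.4) are thresholds on a glucose value. They do not say whether the participant needed help.
2. CGM need not cover the night. SAP 3.4 accepts a session with 144 readings, which it equates to 12 hours, between exercise and noon the next day. Protocol 3.2.3 puts that window at about 24 hours. The overnight period in SAP 3.2 is 10 PM to 8 AM, or 10 hours. That leaves 24 − 10 = 14 other hours, and 14 exceeds 12, so a session can qualify with no overnight data.
3. The instruction to record treatment is in Protocol 3.2.2, on the exercise session itself. After discharge, participants log meals (Protocol 3.2.3), not assistance.
4. The day-after call (Protocol 3.2.3) asks about adverse events. Under 4.1.1 an assisted, orally treated episode is not one, so it need not be recorded even if mentioned.
5. The serious-event route depends on a judgement of seriousness, which an orally treated episode may not meet.
6. The criteria are also uneven. In 4.1.1, a hyperglycemic event counts if a health care provider evaluated or treated it. Hypoglycemia has no such trigger.

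**Injection-site reactions.**

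1. Each participant has three injected sessions: saline in control, saline in strategy 1, glucagon in strategy 3. With 16 completers that is 16 × 1 = 16 glucagon and 16 × 2 = 32 saline injections, 48 in all.
2. The three-point intensity scale in Protocol 4.1.2 applies to adverse events, so untreated reactions are never graded.
3. The earlier site-pain finding is from doses of 500 and 1,000 µg. This trial plans 150 µg, with a possible range of 75–300 µg; the lower rescue dose is 500/300 = 1.7 times the top of that range. For the earlier 75–300 µg study, Protocol 4.2.1 reports nausea and vomiting ("Nausea, but not vomiting was reported by 4/12 subjects given the 300" µg dose) and gives no figure for site pain. The rate at the doses used here is therefore unknown from the documents.

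**Size.** Neither document gives a rate for assisted hypoglycemia or for untreated site reactions. The only available figure is the weight of one participant, 1/16 = 6.25 percentage points. That is a scale, not an estimate of what will be missed.

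**The case against.** The rule is deliberate. Protocol and SAP state it identically, and limiting hypoglycemia and injection AEs to events of some consequence is a common and defensible threshold in a study where low glucose is expected and measured. Hypoglycemia is compared by strategy as an outcome, so the AE table is not the only safety display. Exclusion criterion 1 removes people with a recent severe episode, which should make assisted events rarer. The study is a 16-person feasibility trial with a descriptive primary analysis that does not depend on the AE rule. All of this stands, and it is why the point is minor.

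The documents also rule out four stronger readings that a reader might infer.

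- *Severe hypoglycemia is omitted.* It is not. Episodes needing IV dextrose or IM glucagon are AEs, including IM glucagon given at home, and serious episodes are reportable under 4.1.3.
- *The protocol contradicts its own definition.* The third-party wording is an eligibility criterion about past history. What is missing is an on-study definition.
- *The safety table misses the best-known risks of glucagon.* Nausea and vomiting are reportable without restriction, as are treated site reactions. The site-pain evidence is from healthy volunteers at rescue doses, and Protocol 4.2.1 says edema and erythema were infrequent.
- *Severe events will cluster overnight.* The figure of roughly 50% in Protocol 1.1 concerns young patients, any nocturnal hypoglycemia rather than assisted episodes, 7–11 hours after vigorous afternoon exercise. Here adults exercise moderately in the morning. Even if exercise ends at noon, 7–11 hours later is 7–11 PM, mostly before the SAP's overnight period begins.

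None of this fills the two empty rows. No listed item records whether help was needed, and none collects untreated site reactions.

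**Conclusion.** The point holds in this limited form: as written, the by-strategy AE table cannot show non-serious, orally treated hypoglycemia that required another person's help, or untreated injection-site reactions, and nothing else listed in the plan records them. The number of events lost cannot be estimated from the documents and may be zero for assisted hypoglycemia. The primary comparison is unaffected.

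The conclusion assumes that the case report forms and procedure manual, which are not among the documents, collect no more than the protocol and SAP describe. If they already ask about assistance and site reactions, only the reporting rule and the tables need to change. Severity is low. The case for acting is that the change is cheap and that the design already supplies the glucagon-versus-saline comparison.

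**What to change.** These changes concern recording and reporting only; no treatment rule is involved.

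1. In Protocol 4.1.1 and SAP 4.1.1, add hypoglycemia that required third-party assistance to the reportable events, alongside the existing IV dextrose and IM glucagon criterion. The definition should turn on the participant needing help. Otherwise every dextrose tablet handed over by staff during a session could count.
2. Add one question on such assistance to the existing day-after call.
3. At each of the three injected sessions, record any injection-site reaction (yes/no, and intensity on the existing three-point scale), treated or not. In SAP 4.1.2, tabulate it by strategy, glucagon against saline.

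The SAP's version table says data collection was already in progress. The change can apply only to sessions still to come, so the tables should give the number of sessions recorded under the new rule and footnote the rule in force for the others.

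The cost is matching wording in two documents, one question per call and one form item per injected session. The downside is slightly more data entry and a somewhat higher AE count.
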